7.2.1 Assessment of Severity

The severity, or intensity, of an AE refers to the extent to which an AE affects the participant's daily activities.

All AEs that are reported must have their severity graded. To grade AEs, sites must refer to the Division of AIDS Table for Grading the Severity of Adult and Pediatric Adverse Events (DAIDS AE Grading Table), corrected Version 2.1, July 2017, which can be found on the DAIDS RSC website at:

<https://rsc.niaid.nih.gov/clinical-research-sites/daids-adverse-event-grading-tables>.

7.2.2 Assessment of Causality

If there is any doubt as to whether a clinical observation is an AE, the event should be reported.

The relationship or association of the investigational agent/placebo in causing or contributing to the AE will be characterized using the following classification and criteria:

- Unrelated: There is no association between the investigational agent/placebo and the reported event.

- Related: A causal relationship exists between administration of the investigational agent/placebo and the AE, and other conditions (concurrent illness, progression/expression of disease state, or concurrent medication reaction) do not appear to explain the event.

7.3 Recording Adverse Events

Post entry, the following must be recorded on the eCRFs within 72 hours:

- Grade ≥ 2 AEs
- AEs that led to a change in study treatment/intervention regardless of grade

Post entry, the following must be recorded on the eCRFs within 24 hours:

- AEs meeting SAE definition
- AESIs

Information to be collected includes the following:

- study product group (investigational agent/placebo)
- route of administration
- dose
- event term
- time of onset
- investigator-specified assessment of severity and relationship to the investigational product
- time of resolution of the event
- seriousness
- any required treatment or evaluations
- outcome

Adverse events resulting from concurrent illnesses, reactions to concurrent illnesses, reactions to concurrent medications, or progression of disease states must also be reported. All AEs will be followed to adequate resolution. The MedDRA will be used to code all AEs.

Any medical condition that is present at the time that the participant is screened but does not deteriorate should not be reported as an AE. However, if it deteriorates at any time during the study, it should be recorded as an AE with a descriptive modifier (e.g., "Exacerbation of," "Worsening of," "Deterioration of") the event.

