7.1 Definitions of Adverse Events

Adverse Event

An adverse event (AE) is any unfavorable and unintended sign (including an abnormal laboratory finding), symptom, or diagnosis that occurs in a study participant during the conduct of the study REGARDLESS of the attribution (i.e., relationship of event to medical treatment/investigational agent/device or procedure/intervention). This includes any occurrence that is new in onset or aggravated in severity or frequency from the baseline condition.

The scale used in the Study Diary for participant symptoms does NOT equate to the AE grading as found in the Division of AIDS Table for Grading the Severity of Adult and Pediatric Adverse Events (DAIDS AE Grading Table), corrected Version 2.1, July 2017.

Sites should grade participant symptoms as they normally would according to the DAIDS AE Grading Table.

Serious Adverse Events (SAEs)

An SAE is defined as any untoward medical occurrence that results in any of the following outcomes:

- results in death
- is life-threatening
- requires inpatient hospitalization or prolongation of existing hospitalization
- results in persistent or significant disability/incapacity
- is a congenital anomaly/birth defect.
- is an important medical event that may not be immediately life threatening or result in death or hospitalization but may jeopardize the participant or may require intervention to prevent one of the other outcomes listed in the definition above).

Adverse Events of Special Interest

An adverse event of special interest (AESI) (serious or nonserious) is defined as an AE or SAE of scientific and medical concern specific to the investigational agent, for which ongoing monitoring and rapid communication by the investigator to the sponsor could be appropriate.

See appendix/appendices for AESIs related to specific investigational agents.

Suspected Unexpected Adverse Events

A Suspected Unexpected Serious Adverse Reaction (SUSAR) is defined as a serious adverse reaction, the nature or severity of which is not consistent with the applicable product information (e.g., Investigator's Brochure for an unapproved investigational product).

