7.5 Study Monitoring

The protocol team will monitor the conduct and safety of the study via regular summaries of accrual, study discontinuation, data completeness, and adverse events.

The DAIDS Clinical Representative will review and assess select AE reports for potential impact on the study participant safety and protocol conduct as per DAIDS policies, guidance documents, and SOPs as applicable.

The DSMB will conduct interim reviews for safety. Enrollment will pause and the DSMB will review any death that occurs on study that is deemed related to study product as determined by the site investigator. A pause in enrollment for that study product group (investigational agent/placebo) will also occur and the DSMB will review if two participants experience a Grade 4 AE that is deemed related to study product as determined by the site investigator.

See [section 10.0](#) for statistical and other considerations related to interim monitoring.

Detailed plans for study monitoring are outlined in a Safety Management Plan. See relevant appendix/appendices for additional monitoring procedures.

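### A related Grade 4 AE counts toward the enrollment pause in 7.5 even if it is not serious, but 7.3 gives such an event 72 hours to be recorded rather than 24

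*Protocol*

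**What the plan says.** Protocol section 7.5 has two event-driven triggers for a pause. The first is a related death: "Enrollment will pause and the DSMB will review any death that occurs on study that is deemed related to study product". The second applies to the product group concerned, and operates "if two participants experience a Grade 4 AE that is deemed related to study product as determined by the site investigator". The second trigger depends on grade and relatedness only; seriousness is not a condition.

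Section 7.3 sets two recording deadlines. Under "Post entry, the following must be recorded on the eCRFs within 72 hours" it lists AEs of Grade 2 or higher and AEs that led to a treatment change. Under "Post entry, the following must be recorded on the eCRFs within 24 hours" it lists SAEs and AESIs. Sections 7.3.1 and 7.3.2 repeat the 24-hour rule for those two classes and for no others.

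Section 7.1 defines an AE as "any unfavorable and unintended sign (including an abnormal laboratory finding), symptom, or diagnosis" occurring on study, whatever its cause. It defines an SAE by outcome or medical importance, not by grade.

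Section 8.1 bars further dosing after a related Grade 4 AE. It asks that the protocol team be told within 24 hours when parenteral treatment is stopped, which includes an interrupted single-dose administration, and within 72 hours when non-parenteral treatment is stopped.

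**The concern.** The recording deadlines and the pause rule sort events differently. The pause rule uses grade and relatedness; the 24-hour list uses seriousness and special interest. A related Grade 4 event outside the SAE and AESI classes counts toward the pause but has the slower deadline.

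The timing matters because section 10.5.1 puts the first phase II DSMB review about six weeks after enrollment to an agent starts, with reviews roughly monthly after that. Before the first review and between later ones, the pause in 7.5 is the event-triggered safety stop in the master text. The two participants may be at different sites, in which case neither site can be expected to know that the threshold has been reached. The count is complete only when both events have been recorded, and enrollment to the product group continues until then.

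**Working it through.** No sample size, power or error rate is involved. The check sets the pause rule against the recording rules. One assumption is needed: the deadlines in 7.3 run from the time site staff learn of the event. Section 7.3.1 says so for SAEs; 7.3 does not state a start.

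**Longest permitted recording time for each event that counts in 7.5**

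| Event | Class under 7.1 | Deadline in 7.3 |
|---|---|---|
| Related death | SAE | 24 h |
| Related Grade 4 AE that is an SAE or AESI | SAE or AESI | 24 h |
| Related Grade 4 AE that is neither | Other AE, Grade 2 or higher | 72 h |

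The difference for the last row is 72 − 24 = 48 h.

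**Is the last row empty?** No. Laboratory abnormalities are AEs under 7.1, and Grade 4 is not in itself an SAE criterion. The broadest SAE limb, "is an important medical event that may not be immediately life threatening or result in death or hospitalization but may jeopardize the participant", will capture many Grade 4 events but depends on judgment. A related Grade 4 laboratory value judged not to meet it, and not listed as an AESI, falls in the last row.

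**Does section 8.1 close the gap?** Only in part. Stopping or interrupting a parenteral dose brings a 24-hour notice to the protocol team. After a completed single infusion there is no dosing left to stop, so that notice is not triggered. For a non-parenteral agent the notice period is itself 72 h.

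**How does 48 h compare with the delay in detecting an event?** Neither deadline covers the time from the event to site awareness. Nominal visits through day 28 are days 0, 3, 7, 14 and 28, so the gaps are 3 − 0 = 3, 7 − 3 = 4, 14 − 7 = 7 and 28 − 14 = 14 days. Detection delay can therefore exceed 48 h, and a change to the recording deadline does not alter it.

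**Fax back-up (separate point).** Section 7.3.1 requires SAE reports within 24 hours of awareness, but its fax route, used when electronic submission is not possible, allows one business day. Section 7.3.2 uses the same route for AESIs. Taking one business day as the same clock time on the next business day:

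- awareness Monday to Thursday, with the next day a business day: 24 h, excess 24 − 24 = 0 h;
- Friday 18:00 to Monday 18:00: 72 h, excess 72 − 24 = 48 h;
- Friday 18:00 to Tuesday 18:00, with Monday a public holiday: 96 h, excess 96 − 24 = 72 h.

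**The case against.** The two sections do not contradict each other. Section 7.5 sets a threshold and no reporting deadline, and a site can comply with both sections as written. Section 7.0 sends the reader to the agent appendices for changes to AE recording and to the manual of procedures for reporting instructions, and 7.5 adds that "Detailed plans for study monitoring are outlined in a Safety Management Plan". None of these is available here; any of them may already require a 24-hour alert, and the appendices also define the AESIs and the hematology and chemistry testing. What remains after SAEs, AESIs and stopped parenteral dosing is small, and the causality definition in 7.2.2 is strict. The 72 hours is a maximum, detection delay may be longer, and 7.5 also provides for regular team summaries and sponsor-side review of selected AE reports. The fax point arises only when the electronic system fails.

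Most of this stands and limits the weight of the point: the class is narrow, its frequency is unknown, and no number of participants exposed can be given. It does not remove the mismatch. The master text is not silent; it states a 72-hour requirement for events that its own pause rule counts, and nothing in the text shown shortens it. A general pointer to other documents does not tell a site that this class is urgent.

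**Conclusion.** The point holds. As the protocol is written, a fully compliant site may record one kind of pause-counting event 48 hours later than it must record an SAE. This is a poorly matched deadline on a safety stop, not a numerical error, and it does not affect the analysis.

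The conclusion assumes that the 7.3 deadlines run from site awareness and that no appendix, manual or Safety Management Plan already sets a faster alert. It applies to related Grade 4 AEs that are neither SAEs nor AESIs, arising after a completed infusion or with a non-parenteral agent. Because neither the frequency of such events nor the enrollment rate is stated, the effect can be given only as a time. The change is worth making because it supports a safety stop at almost no cost.

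The fax back-up is a separate, minor inconsistency. On the stated reading of a business day, it can exceed the 24-hour rule by 48 to 72 hours over a weekend.

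**What to change.** In section 7.3, add Grade 4 AEs assessed by the site investigator as related to study product to the 24-hour list, so that both pause triggers in 7.5 carry the same deadline. It would help to state there that the clock starts at site awareness. If an appendix, the manual of procedures or the Safety Management Plan already sets a 24-hour alert for these events, a specific cross-reference in 7.3 is enough. In section 7.3.1, set the fax back-up deadline to 24 hours after awareness.

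The cost is one bullet, one changed deadline and slightly faster site reporting for what is likely a rare class of event. The AE form already collects the "investigator-specified assessment of severity and relationship to the investigational product", so an automatic alert can use existing fields. The pause threshold, dosing rules, sample size and analyses stay as they are.

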7.3.1 Reporting Serious Adverse Events

Any AE that meets SAE criteria must be reported to PPD, Inc., immediately (i.e., within 24 hours of the time that the site personnel first learn about the event) by indicating on the Adverse Event eCRF within the Electronic Data Capture (EDC) system that seriousness criteria is met and providing initial relatedness/causality.

In the event the EDC electronic submission is not possible, a completed SAE/AESI report form along with written description of the serious adverse experience must be sent to PPD PVG by facsimile within 1 business day after awareness of the event (see regional Fax numbers below). Please note, the event must be entered into EDC once access has been corrected.

PPD Safety Reporting Fax Number
NA: [contact]
LA: [contact]
EMEA/APAC: [name]

The following contact information is to be used for inquiries to determine if an event is reportable as an SAE:

PPD Safety Hotline Phone Number
NA (RTP): [contact]
LA: [contact]
EMEA/APAC: [name]

The sponsor has a legal responsibility to notify the US FDA and other regulatory agencies about the safety of an investigational product under clinical investigation. The sponsor will comply with country-specific regulatory requirements relating to safety reporting to the regulatory authority, institutional review board/independent ethics committee (IRB/IEC), and investigators.

An investigator who receives an investigator safety report or memorandum describing an SAE or other specific safety information from the sponsor will review and then file it as appropriate and will notify the IRB/IEC and local regulatory agencies, if appropriate according to local requirements.

7.3.2 Reporting Adverse Events of Special Interest

Any AE that meets AESI criteria ([section 7.1](#)) must be reported immediately (i.e., within 24 hours of the time that the site personnel first learn about the event) by indicating on the Adverse Event eCRF that AESI criteria are met. If electronic submission is not possible it can be submitted in the same manner as the back-up manual SAE/AESI reporting process ([section 7.3.1](#)).

Contact the PPD Safety Hotline Phone Number with any questions on reportability.

7.3.3 Reporting Suspected Unexpected Serious Adverse Reactions

The sponsor will promptly evaluate all SUSARs and nonserious AEs of special interest (defined in [section 7.1](#)) against cumulative product experience to identify and expeditiously communicate possible new safety findings to investigators, IRBs/IECs, and applicable health authorities based on applicable legislation.

To determine reporting requirements for single AE cases, the sponsor will assess the expectedness of these events using the investigational agent Investigator's Brochure.

The sponsor will compare the severity of each SUSAR and the cumulative event frequency reported for the study with the severity and frequency reported in the applicable reference document.

Reporting requirements will also be based on the investigator's assessment of causality and seriousness, with allowance for upgrading by the sponsor as needed.

7.4 Follow-up of Participants Reporting Adverse Events

All AEs must be reported in detail on the appropriate page in the eCRF and followed to satisfactory resolution, until the investigator deems the event to be chronic or not clinically significant, the event is considered to be stable, or the participant is lost to follow-up.

7.5 Study Monitoring

The protocol team will monitor the conduct and safety of the study via regular summaries of accrual, study discontinuation, data completeness, and adverse events.

The DAIDS Clinical Representative will review and assess select AE reports for potential impact on the study participant safety and protocol conduct as per DAIDS policies, guidance documents, and SOPs as applicable.

The DSMB will conduct interim reviews for safety. Enrollment will pause and the DSMB will review any death that occurs on study that is deemed related to study product as determined by the site investigator. A pause in enrollment for that study product group (investigational agent/placebo) will also occur and the DSMB will review if two participants experience a Grade 4 AE that is deemed related to study product as determined by the site investigator.

See [section 10.0](#) for statistical and other considerations related to interim monitoring.

Detailed plans for study monitoring are outlined in a Safety Management Plan. See relevant appendix/appendices for additional monitoring procedures.

8.0 CLINICAL MANAGEMENT ISSUES

The following guidance pertains to all investigational agents; however, additional guidance for particular agents are included in the appendix relevant for each investigational agent.

8.1 Toxicity

Criteria for participant management, dose adjustments and discontinuation, or changes in treatment will be described only for toxicities attributable to the investigational agents, when applicable, and are included in the appendix/appendices.

The grading system for drug toxicities is located in the Division of AIDS Table for Grading the Severity of Adult and Pediatric Adverse Events (DAIDS AE Grading Table), corrected Version 2.1, July 2017, which can be found on the DAIDS RSC website at <https://rsc.niaid.nih.gov/clinical-research-sites/daids-adverse-event-grading-tables>.

NOTE: The protocol team must be notified within 72 hours regarding toxicities that result in a change in study regimen (follow the directions described in the [Study Management section](#)).

For all agents evaluated in this trial, if a participant develops a Grade 4 AE that is related to the study product as determined by the site investigator, no further doses of the study treatment should be administered.

It is possible that some participants will experience transient or prolonged AEs during the study. As some of the visits will be conducted remotely, AEs will often be assessed remotely and unplanned study visits scheduled if deemed necessary by the site investigator. For any concerning AEs that are felt to require clinical intervention, participants should be instructed to contact their health care provider or seek urgent or emergent care, or 911 should be called, as appropriate.

Treatment may be discontinued without contacting the protocol team in advance, but the protocol team should be notified within 24 hours of parenteral and 72 hours of **non-parenteral** treatment discontinuation (follow the directions described in the [Study Management section](#)). This includes an interruption in administration for single-dosed agents.

8.2 Management of Side Effects

See relevant appendix/appendices for additional details on the management of side effects.

8.2.1 Overdose

An overdose is any dose of study treatment given to a participant or taken by a participant that exceeds the dose described in the protocol.

Any overdose must be reported to the PPD Drug Safety Center within 24 hours (follow the directions described in the [Study Management section](#)). The overdose itself is not to be reported as an AE. However, any AEs associated with the overdose are to be reported on relevant AE/SAE sections in the eCRF.

In the event of an overdose, the site investigator should:

1. Contact the protocol team immediately (follow the directions described in the [Study Management section](#)).
2. Closely monitor the participant for any AE/SAE and laboratory abnormalities.
3. Obtain a plasma sample for PK analysis within 3 days from the date of the last dose of investigational agent/placebo if requested by the medical monitor.
4. Document the quantity of the excess dose as well as the duration of the overdose in the eCRF.

Decisions regarding dose interruptions or modifications will be made by the site investigator in consultation with the medical monitor based on the clinical evaluation of the participant.

8.3 Pregnancy

The use of investigational agents in pregnancy will vary depending upon agent. The ability to continue or need to discontinue investigational agent in event of pregnancy is outlined in the relevant appendix/appendices.

8.4 Breastfeeding

The use of investigational agent in breastfeeding participants who meet inclusion criteria for the study will vary depending upon agent and is outlined in the relevant appendix/appendices.

9.0 CRITERIA FOR DISCONTINUATION

Participants may discontinue from the investigational product or withdraw from the study at any time and for any reason without prejudice to their future medical care by the investigator or at the study site. Every effort should be made to keep participants in the study. The reasons for participants discontinuing the investigational product and/or withdrawing from the study will be recorded on an eCRF.

9.1 Permanent and Premature Treatment Discontinuation

- Drug-related toxicity mandating discontinuation (see appendix/appendices).
- Participant experiencing an SAE that is considered related to investigational agent.
- Requirement for prohibited concomitant medications (see [section 5.4](#) and relevant appendix/appendices).
- Request by participant to terminate treatment.
NOTE: The reason for treatment discontinuation should be documented (e.g., concern for AE, lack of efficacy, or other reason).
- Clinical reasons believed life threatening by site clinical staff, even if not addressed in the [Toxicity section](#) of the protocol.
- Any additional indications are outlined in the relevant appendix/appendices.

9.2 Premature Study Discontinuation

- Failure to initiate investigational agent.
- Request by the participant to withdraw consent.
- Request of the health care provider if they think the study is no longer in the best interest of the participant.
- At the discretion of the IRB/EC, FDA, NIAID, ACTG, Office for Human Research Protections (OHRP), other government agencies as part of their duties, investigator, or industry supporter.
- Any additional indications are outlined in the relevant appendix/appendices.

In the event that a participant prematurely discontinues from the study, unless they have withdrawn consent or never initiated investigational agent/placebo, sites will attempt to obtain information regarding vital status (including date last seen alive, hospitalization, date of death, and primary cause of death) from other sources (e.g., family members, other designated secondary contacts, or clinic records). See the MOP for further guidance.

